Title	PATCH 2 & 3: (Prevention and Treatment of COVID-19 with Hydroxychloroquine) A double-blind placebo controlled randomized trial of hydroxychloroquine in the prevention and treatment of COVID-19
Protocol Number	2020-0003
Phase	Phase II
Methodology	Double-blind placebo controlled randomized prevention and treatment trial
Study Duration	1 year
Study Center(s)	Virtual trial based out of a clinical research institution – ProHealth NY
Objectives	
PRIMARY OBJECTIVES: PATCH 2 (Sub-Study 1, Patients tested for COVID-19 who meet symptomology and age requirements for eligibility): Rate of hospitalization
 
PATCH 3 (Sub-Study 2, Health Care Workers): Rate of COVID-19 infection (confirmed by accepted testing methods) over two months (60 days)
 
SECONDARY OBJECTIVES PATCH 2 (Sub-Study 1): Rate of secondary infection of co-inhabitants, adverse events, and negative for COVID-19 (confirmed by accepted testing methods) at 14 days
 
PATCH 3 (Sub-Study 2): Number of shifts missed, rate of adverse events, and hospitalization

Number of Subjects	
PATCH 2 (Sub-Study 1): 500 with interim analysis at time points corresponding to 34% and 68% of the desired sample size
 
*PATCH 3 (Sub-Study 2): 350 with interim analysis at time points corresponding 25% and 50% of the desired total sample size
 
Total: 850
 
*Eventual expectation for needing 100% crossover

Diagnosis and Main Inclusion/Exclusion Criteria	
PATCH 2 and PATCH 3 Inclusion Criteria
 
 • Willing and able to provide informed electronic consent via DocuSign

	
 • Willing to report compliance with HCQ or Placebo (“tablets”) in the form of an on-line journal and participate in other forms of self-reporting (e.g., symptom tracker and experience log) • Willing and able to go to designated areas for testing (COVID-19/SARS-CoV-2 and/or serologic) and/or administer at home testing kits for study data collection purposes. • Must be able to swallow and retain oral medication and must not have any clinically significant gastrointestinal abnormalities that may alter absorption such as malabsorption syndrome or major resection of the stomach or bowels • Must have adequate baseline organ function • Subjects meeting the following criteria by Sub-Study: 
PATCH 2 Inclusion (Sub-Study 1): 50-75 years of age; self-reporting as having a fever within four days prior to time of enrollment; and not requiring hospitalization. Enrolled individuals will undergo testing for COVID-19 and return home for self-quarantine. Patient must be willing and able to provide informed consent, agree to testing for COVID-19 at time of enrollment to confirm diagnosis, at the end of treatment (Day 15, 16 or 17) and two weeks after the end of treatment (Day 29, 30 or 31) where Day 1 is defined as the first day blinded study drug is taken by the patient. (See Appendix- PATCH2 process flows)
 
PATCH 3 Inclusion (Sub-Study 2): Currently employed as a health care worker ([name]; Doctor of Osteopathic Medicine, DO; Nurse Practitioner, NP; Physician’s Assistant, PA; and [name] or other members of the medical care team with significant COVID-19 exposure); asymptomatic and presumed negative for COVID-19 (no confirmatory testing conducted); scheduled for an average of ≥ 20 hours per week of clinical care over the next two months (or equivalent indicating at least part-time employment). Participant will be asked to comply with their employer’s potential or confirmed COVID-19 incident protocol and must agree to undergo COVID-19 testing per standard of care using an FDA approved method upon the presentation of symptoms indicative of an influenza like illness; if a confirmatory COVID-19 diagnosis is given, participant will be offered to cross-over to HCQ 600 mg qd for 14 days. At the end of the 60-day medication period, participants remaining undiagnosed for COVID-19 will undergo virus and serology testing. (See Appendix- PATCH3 process flows)

--	---

	
PATCH 2 & PATCH 3 Combined Exclusion Criteria (See Study Exclusions and Content Job Aid)
 
 • Allergy to hydroxychloroquine, 4 aminoquinolines, or quinine • Known G6PD deficiency • Pregnant or lactating or intention of becoming pregnant during the study as self-reported during enrollment screening • Receiving any trial treatment drug for 2019-nCoV within 14 days prior to screening evaluation (off label, compassionate use or trial related) • Known retinal disease including but not limited to macular degeneration, retinal vein occlusion, visual field defect, diabetic retinopathy • History of interstitial lung disease severe emphysema or asthma, or chronic pneumonitis Current diagnosis of porphyria or psoriasis • Serious intercurrent illness that requires active intravenous therapy, intense monitoring, or frequent dose adjustments for medication including but not limited to infectious disease, cancer, autoimmune disease, cardiovascular disease • Have undergone major abdominal, thoracic, spine or CNS surgery in the last two months, or plan to undergo surgery during study participation • Is receiving cytochrome P450 enzyme-inducing anticonvulsant drugs (i.e. phenytoin, carbamazepine, Phenobarbital, primidone or oxcarbazepine) within four weeks of the start of the study treatment • Currently taking digoxin • History or evidence of increased cardiovascular risk including any of the following: 
 ○ Left ventricular ejection fraction (LVEF) < institutional lower limit of normal. Baseline echocardiogram is not required ○ Current clinically significant uncontrolled arrhythmias. Exception: Subjects with controlled atrial fibrillation ○ History of acute coronary syndromes (including myocardial infarction and unstable angina), coronary angioplasty, or stenting within 6 months prior to enrollment ○ Current \geq Class II congestive heart failure as defined by New York Heart Association
--	--

PATCH 2 & 3 TRIAL

	
 Deemed unable to participate for medical reasons identified by Co-PI and study staff
Study Product, Dose, Route, Regimen	Hydroxychloroquine, various doses, oral Matching placebo, oral
Duration of administration	
PATCH 2 (Sub-Study 1): COVID-19 patients in self-quarantine. Arm 1: HCQ 400 mg bid (two 200 mg tablets taken twice a day; totaling 800 mg per day) for 14 days Arm 2: Placebo 2 pills bid for 14 days
 
PATCH 3 (Sub-Study 2): Asymptomatic health care worker prophylaxis. Arm 1: HCQ 600 mg qd (three 200 mg tablets taken once a day) for up to 60 days Arm 2: Placebo 3 pills qd for up to 60 days; cross-over from placebo to HCQ 600 mg qd for 14 days is allowed upon confirmatory diagnosis for COVID-19

Study design	1:1 randomization in each cohort between the arms
Duration of trial	Approximately 1 year

1.0 OBJECTIVES

1.1 Primary Objectives

PATCH 2 (Sub-Study 1): Rate of hospitalization

PATCH 3 (Sub-Study 2): Rate of COVID-19 infection (confirmed by accepted testing methods) over two months

1.2 Secondary Objectives

PATCH 2 (Sub-Study 1): Rate of secondary infections for co-inhabitants, rate of adverse events (AEs), and rate of COVID-19 negativity (confirmed by accepted testing methods) after 14 days of treatment

PATCH 3 (Sub-Study 2): Number of shifts missed, rate of hospitalization, and rate of adverse events (AEs)

2.0 BACKGROUND AND RATIONALE

2.1 Overview of SARS-CoV-2 and Chloroquine Derivatives

Chloroquine derivatives show preclinical efficacy against coronavirus but very little clinical data is available. Emerging viral diseases (EVDs) encompass a growing list of zoonotic viruses that have a major impact on global health and economics. These include Ebola, SARS, MERs, Marburg, and the recently identified virus that causes COVID-19 disease (Wuhan Coronavirus: SARS-CoV-2) (1). In each of these cases there is currently no effective drug treatments or prophylaxis agents that can be quickly applied to large populations at risk for the virus. As of March 2020, The SARS-CoV-2 virus has infected more than 180,000 people causing more than 5000 deaths. This has led to a lockdown of entire megacities in China, international travel bans, and disruptions in global supply chains. More alarming is the recent evidence that health care workers are getting infected and dying of the virus, wreaking havoc on the chain of care. In addition, while prior epidemics such as Ebola seemed to be contained in Africa, the current COVID-19 global crisis demonstrates how with the extent of globalization and international travel, no country is safe from these EVDs.

Coronaviruses are a large family of viruses that commonly infect many animals, including camels, cattle, cats, and are often found in bats as their zoonotic reservoir. While it is rare, animal coronaviruses can infect people and then spread between people, as had occurred with Middle East respiratory coronavirus (MERS-CoV) and severe acute respiratory coronavirus (SARS-CoV), and now the newly emerged coronavirus SARS-CoV-2 (also known as COVID-19). The SARS-CoV-2 virus is a betacoronavirus, like MERS-CoV and SARS-CoV. All three of these viruses have their origins in bats. While SARS-CoV and MERS-CoV exhibit significantly higher mortality than SARS-CoV-2, the ability to spread between humans is less than SARS-CoV-2. There is emerging evidence from Asia that patients can be highly contagious with one patient spreading viral particles to 87% of 15 sites within the patient's room. Virus can be shed in urine and feces as well as respiratory secretions increasing the likelihood that sick contacts and hospital staff will become infected (2). An epidemiological survey of 72,000 cases in China found an overall 3.8% infection rate in hospital workers, but a 68% infection rate of hospital workers in Wuhan at the epicenter of disease. This suggests that if low rates of infection are in a community, the likelihood of hospital workers contracting disease is low, but if there are a large number of cases then the likelihood of hospital workers contracting the disease is high (3). Patients above the age of 50 are more likely to die of this disease and the time from diagnosis to death can occur within one month despite access to high-level intensive care units (4). A high rate of intra-family transmission and rapid community transmission has been documented in Shenzhen China (5). Meanwhile a screen of compounds found that chloroquine prevented and eradicated established infection of SARS-CoV-2 virus in vitro. I was contacted by researchers in China who indicated that 8/10 coronavirus infected patients treated with chloroquine 500 mg daily cleared their virus. The hospital ran out of chloroquine, and they have had to turn to other means of treating the virus. We believe hydroxychloroquine is a safer drug than chloroquine and affords the ability to dose escalate to concentrations that we know are effective at blocking the lysosome in patients.

Our *hypothesis* is that high doses of hydroxychloroquine for at least 2 weeks can be effective antiviral medication both as a treatment in ambulatory patients and prophylaxis/treatment in health care workers because it impairs lysosomal function and reorganizes lipid raft (cholesterol and sphingolipid rich microdomains in the plasma membrane) content in cells, which are both critical determinants of EVD infection. This hypothesis is based on a growing literature linking chloroquine to antiviral activity. We believe there is enough information to launch a clinical trial of hydroxychloroquine for COVID-19.

2.2 Mechanistic rationale for antiviral properties of chloroquine derivatives

2.2a Coronaviruses. Coronaviruses (CoV) infect mammals and birds causing respiratory, gastrointestinal, and central nervous system diseases. Coronavirus virions contain an envelope, a helical capsid, and a single-stranded RNA genome, the largest among all RNA viruses. The name “coronaviruses” derives from the spike proteins on their envelope that give the virions a crown-like shape. CoVs include the following: 1) α -genus: human coronavirus NL63 (HCoV-NL63), porcine transmissible gastroenteritis coronavirus (TGEV), and porcine respiratory coronavirus (PRCV) 2) β -genus: SARS-CoV-2/COVID-19, severe acute respiratory syndrome coronavirus (SARS-CoV), Middle East respiratory syndrome coronavirus (MERS-CoV), mouse hepatitis coronavirus (MHV), and bovine coronavirus (BCoV). 3) CoVs of the γ -genus include avian infectious bronchitis virus (IBV) and do not infect humans so are valuable laboratory agents (6). Coronaviruses impose health threats to humans and animals. SARS-CoV caused the SARS epidemic in 2002 to 2003, with over 8,000 infections and a fatality rate of ~10%. MERS-CoV emerged from the Middle East in 2012 causing 877 infections with a fatality rate of ~36%. HCoV-NL63 from the α -genus is a widespread pathogen that produces the common cold in healthy adults and acute respiratory illness in young children. CoVs are also major animal pathogens. TGEV and MHV cause close to 100% fatality in young pigs and young mice, respectively; BCoV and IBV also cause significant healthcare burden for domesticated cattle and chickens, respectively. Therefore, research on coronaviruses has strong health and economic implications (6).

2.2b CoV infection requires functional lysosomes. Receptor recognition by viruses is the first and essential step of viral infections of host cells. An envelope-anchored spike protein mediates coronavirus entry into host cells by first binding to a receptor on the host cell surface and then fusing viral and host membranes. CoVs recognize a number of different host receptors. Once the receptor is bound, there is viral and cell membrane fusion, followed by endocytosis and lysosomal processing. CoVs like SARS enter the cell through lipid raft enriched endocytosis (7). The details of the interaction between the virus spike protein, virus membrane and the lipid rafts are not worked out. In the lipid raft literature, it is often the case that lipid rafts (semisolid phase membrane filled with cholesterol and sphingolipids) are only physiologically functional if there is a non-lipid raft membrane region next to it. After membrane fusion, endosomal pH acidification is a fusion trigger for CoVs and other viruses including influenza virus and vesicular stomatitis virus (VSV). For instance the use of lysosomal inhibitor blocked the entry of the model coronavirus IBV (8). The authors directly assessed the pH dependence of IBV fusion and found that fusion only occurs at acidic pH. For some CoVs that harbor a non-cleaved spike protein on their surface, such as MHV-2 and SARS-CoV, it has been shown that they rely on lysosomal proteases for productive entry. In fact one study found that bat cells have more efficient lysosomal proteolysis than human cells providing an explanation for why bats are preferred zoonotic hosts for CoVs (9).

2.2c Evidence that chloroquine prevents coronavirus infection. It has been reported that chloroquine has strong antiviral effects on SARS-CoV infection and spread in vitro (10-12). In to increasing endosomal/lysosomal pH, these studies demonstrated that CQ abrogates glycosylation of ACE2, the cellular receptor of SARS-CoV, which may contribute further to infection suppression. The IC₅₀ of chloroquine for inhibition of SARS-CoV in vitro is 8.8 micromolar which would require higher concentrations than typically delivered in malaria. Importantly, the suppressive effects are observed when the cells are treated with chloroquine either before or after exposure to the virus, suggesting both prophylactic and therapeutic treatment paradigms could be employed (10, 11). The work by Kayaerts looked at human coronavirus OC43 which causes neonatal death in mice. Treatment with chloroquine of pregnant mothers provided a 98.6% protection against death in newborn mice. This is in the only in vivo demonstration of chloroquine efficacy against a CoV. DeWilde et al. screened a library of 348 FDA-approved drugs for anti- MERS-CoV activity in cell culture and only four compounds (chloroquine, chlorpromazine, loperamide, and lopinavir) were found to inhibit the viral replication (50% effective concentrations, EC₅₀ 3–8 $\mu\text{mol/L}$) (12). The protective activity of chloroquine against CoVs such as SARS, MERS and COVID-19 has not yet been established in animal models.

2.2d Chloroquine is active against COVID-19/ SARS-CoV-2: A recent paper from Wuhan China isolated SARS-CoV-2 (the virus that causes COVID-19 disease) and tested 6 modern antiviral drugs and chloroquine and found that the best suppressors of viral infection were remdesivir (IC₅₀ 0.77 μmol) and chloroquine (IC₅₀ 1 μmol) (13). Only chloroquine given at 10 μM was able to suppress infection either with pretreatment, at the time

PATCH 2 & 3 TRIAL

of infection, or after infection occurred. This has led to clinical trials and off label use of chloroquine in China ([name] personal communication with scientists in China). There are Chinese guidelines for the use of chloroquine 500 mg bid for the treatment of COVID-19 (Ref). In addition, an update provided by Chinese physicians suggests initial experience with chloroquine and/or hydroxychloroquine have been positive (ref). Hospitals have run out of chloroquine, and doctors are not confident on proper dosing of hydroxychloroquine. Careful clinical trials with optimized chloroquine derivatives would be well received in a hot zone.

2.3 Clinical experience with high dose hydroxychloroquine in cancer patients

In contrast to CQ, which can produce blindness at high cumulative doses, our recent body of work has demonstrated that high dose HCQ can be administered safely to humans for months. Our work on autophagy as a resistance mechanism to cancer therapy had identified CQ derivatives as potential anti-cancer agents (14). Since HCQ has had a longer track record of dose escalation and chronic dosing in rheumatoid arthritis and lupus, we chose HCQ as our lysosomal autophagy inhibitor to test in combination regimens in cancer patients. We reported the first 6 phase I dose escalation clinical trials involving HCQ in combination with FDA approved anti-cancer drugs in refractory stage IV cancer patients (15-20). In most patients on these trials we were able to escalate the dose of HCQ to 1200 mg per day and dose patients in some cases safely for more than one year. In over 220 patients treated across multiple studies the rate of grade 3-4 non-hematological toxicities was < 10%. Most of these had more to do with the severity of the cancer and would likely not be seen in a healthy population. Specifically, no retinal, cardiac, neurological, hepatic or renal toxicity was observed. Hematological toxicities could be attributed to the other cancer drug (chemotherapy) that HCQ was paired with, and the most common side effects included manageable gastrointestinal symptoms such as bloating, diarrhea, constipation and mild non-bloody diarrhea.

2.4 Low dose versus high dose HCQ

In HCQ studies in cancer patients we conducted population pharmacokinetic studies and pharmacodynamic studies and determined that 800-1200 mg daily was required to effectively and consistently impair the lysosome in peripheral blood mononuclear cells. Our PK studies determined that it took roughly 2 weeks to achieve steady state in cancer patients. For these reasons there is rationale to propose a high dose (600 mg po bid) prolonged schedule treatment (2 weeks). In contrast an in vitro study recently published which included PK-PD modeling extrapolated from published PK studies indicated that HCQ was very active against COVID-19 but only 400 mg po bid X1 followed by 200 mg po bid for 5-10 days was enough for treatment. A recent non-randomized open label French trial Geuret et al Int J Antimicrobial Agents 2020) showed that 600 mg qd of HCQ cleared virus in 70 % of mildly ill hospitalized patients compared to 12.5% at 6 days of control patients. This generates a major question in how to use this agent in different populations that can best be answered in this two-part placebo controlled randomized trial.

3.0 PARTICIPANT SELECTION

The inclusion and exclusion criteria apply to both patient (PATCH 2) and health care worker (PATCH 3) populations unless indicated otherwise.

3.1 PATCH 2 and PATCH 3 Inclusion Criteria (See Study Process Flows)

- Willing and able to provide informed electronic consent via DocuSign
- Willing to report compliance with HCQ or Placebo (“tablets”) in the form of an on-line journal and participate in other forms of self-reporting (e.g., symptom tracker and experience log)

PATCH 2 & 3 TRIAL

- Willing and able to go to designated areas for testing (COVID-19/SARS-CoV-2 and/or serologic) and/or administer at home testing kits for study data collection purposes.
- Must be able to swallow and retain oral medication and must not have any clinically significant gastrointestinal abnormalities that may alter absorption such as malabsorption syndrome or major resection of the stomach or bowels
- Must have adequate baseline organ function
- Subjects meeting the following criteria by Sub-Study:

PATCH 2 Inclusion (Sub-Study 1): 50-75 years of age; self-reporting as having a fever within four days prior to time of enrollment; and not requiring hospitalization. Enrolled individuals will undergo testing for COVID-19 and sent home for self-quarantine. Patient must be willing and able to provide informed consent, agree to testing for COVID-19 at time of enrollment to confirm diagnosis, at the end of treatment (Day 15, 16 or 17) and two weeks after the end treatment (Day 29, 30 or 31) where Day 1 is defined as the first day blinded study drug is taken by the patient. (See Appendix- PATCH2 process flows)

PATCH 3 Inclusion (Sub-Study 2): Currently employed as a health care worker ([name]; Doctor of Osteopathic Medicine, DO; Nurse Practitioner, NP; Physician's Assistant, PA; and [name] or other members of the medical care team with significant COVID-19 exposure); asymptomatic and presumed negative for COVID-19 (no confirmatory testing conducted); scheduled for an average of ≥ 20 hours per week of clinical care over the next two months (or equivalent indicating at least part-time employment). Participant will be asked to comply with their employer's potential or confirmed COVID-19 incident protocol and must agree to undergo COVID-19 testing per standard of care using an FDA approved method upon the presentation of symptoms indicative of an influenza like illness; if a confirmatory COVID-19 diagnosis is given, participant will be offered to cross-over to HCQ 600 mg qd for 14 days. At the end of the 60-day medication period, participants remaining undiagnosed for COVID-19 will undergo virus and serology testing. (See Appendix- PATCH3 process flows)

PATCH 2 & PATCH 3 Combined Exclusion Criteria

(See Study Exclusions and Content Job Aid)

- Allergy to hydroxychloroquine, 4 aminoquinolines, or quinine
- Known G6PD deficiency
- Pregnant or lactating or intention of becoming pregnant during the study as self-reported during enrollment screening
- Receiving any trial treatment drug for 2019-nCoV within 14 days prior to screening evaluation (off label, compassionate use or trial related)
- Known retinal disease including but not limited to macular degeneration, retinal vein occlusion, visual field defect, diabetic retinopathy
- History of interstitial lung disease severe emphysema or asthma, or chronic pneumonitis Current diagnosis of porphyria or psoriasis
- Serious intercurrent illness that requires active intravenous therapy, intense monitoring, or frequent dose adjustments for medication including but not limited to infectious disease, cancer, autoimmune disease, cardiovascular disease

PATCH 2 & 3 TRIAL

- Have undergone major abdominal, thoracic, spine or CNS surgery in the last two months, or plan to undergo surgery during study participation
- Is receiving cytochrome P450 enzyme-inducing anticonvulsant drugs (i.e. phenytoin, carbamazepine, Phenobarbital, primidone or oxcarbazepine) within four weeks of the start of the study treatment
- Currently taking digoxin
- History or evidence of increased cardiovascular risk including any of the following:
 - Left ventricular ejection fraction (LVEF) < institutional lower limit of normal. Baseline echocardiogram is not required
 - Current clinically significant uncontrolled arrhythmias. Exception: Subjects with controlled atrial fibrillation
 - History of acute coronary syndromes (including myocardial infarction and unstable angina), coronary angioplasty, or stenting within 6 months prior to enrollment
 - Current \geq Class II congestive heart failure as defined by New York Heart Association
- Deemed unable to participate for medical reasons identified by Co-PI and study staff

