COVID-19/SARS-CoV-2 testing: Upon the presentation of symptoms indicative of an influenza like illness, participants will be asked to undergo testing for SARS-CoV-2 virus. Participants undiagnosed for COVID-19 at Day 60 will also be tested for SARS-CoV-2 and IgM/IgG antibodies (via serology testing) on either Day 61, 62, or 63.

Clinical Symptom monitoring: The study team will assess AEs, symptoms, and record temperature (either reported temperature or self-report of fever) for any participants taking active medication (placebo or HCQ). Worsening COVID symptoms and/or new or worsening AE's will be reviewed by the PI's for causality to study drug. The rate of conversion to receiving a positive COVID-19 test result in each arm at the 2-month mark will be used to assess the primary endpoint.

Pill count and Journal: Participants will be contacted to compare data entry on the portal and collect any missed entries over the phone.

Participants will be instructed to call 911 upon immediate presentation of the following symptoms as identified by the CDC as requiring emergency action: bluish lips or face; new confusion/dizziness or inability to arouse; persistent pain or pressure in the chest (not caused by coughing); and difficulty breathing (including severe shortness of breath and single word speech).

Participant confidentiality is strictly held in trust by all personnel granted access to the trial data. Therefore, the study data, and all other information generated will be held in strict confidence. No information concerning the study, or the data will be released to unauthorized parties.

The study investigators and study team, the research sponsor and its designees, personnel from ProHealth with authorized access to study data, government agencies, reviewing Institutional Review Board (IRB), regulatory agencies and/or company supplying study product may inspect all documents and records required to be maintained by the sponsor, including but not limited to, clinical, pharmacy and lab records for participants enrolled in the study. All applicable parties will permit access to such records.

The participant's study contact information will be securely stored within the online study portal for internal use during the study. At the end of the study, all records will continue to be kept in a secure location for as long as dictated by the reviewing IRB and institutional policies.

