15.0 MEASUREMENT OF EFFECT

15.1 Definitions

Evaluable for toxicity: All participants will be evaluable for toxicity from the time of their first treatment with HCQ or placebo through final assessment.

Evaluable for primary outcome: Participants who received at least one continuous week of HCQ will be evaluable for the primary outcome.

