Appendix 4: PATCH 3 Job Aid

PATCH3 STUDY LEAD JOB AID

A PATCH3 AUTOMATIC STUDY EXCLUSIONS	
Consumer Language for Enrollment Exclusions 
 These exclusions are automatic during the online enrollment experience in the enrollment portal If indicated exclusion response is selected, it is an automatic exclusion from the study 	Automatic Portal Exclusion
Are you a health care worker scheduled to working an average of 20 hours a week for the next 2 months?	If NO
Are you currently asymptomatic and presume not to have COVID?	If NO
Have you had a fever within the last four days? [yes/ no]	If NO
Do you require hospitalization? [yes/ no]	If YES
Are you able to self-quarantine at home for 14 days? [yes/ no]	If NO
Have you been tested for COVID-19? [yes/ no]	If NO

B AUTOMATIC CLINICAL EXCLUSIONS		
Consumer Language for Enrollment Exclusions 
 These exclusions are automatic during the online enrollment experience in the enrollment portal If “yes” to any, it is an automatic exclusion from the study. 	Automatic Portal Exclusion	
Protocol Language: Allergy to hydroxychloroquine, 4 aminoquinolines, or quinine	Do you have an allergy to hydroxychloroquine (HCQ), aminoquinolines, or quinine? [yes/ no]	X
Protocol Language: Patients with G6PD deficiency	Do you have a G6PD deficiency? [yes/ no]	X
Protocol Language: Pregnant or lactating or positive pregnancy test during pre-medication examination	Are you pregnant? [yes/ no]	X
	Are you breast feeding? [yes/ no]	X
Protocol Language: Receiving any trial treatment drug for 2019-ncov within 14 days prior to screening evaluation (off label, compassionate use or trial related)	Have you been in any other drug trial for COVID-19? [yes/ no]	X
Protocol Language: Patients with serious intercurrent illness that requires active infusional therapy, intense monitoring, or frequent dose adjustments for medication including but not limited to infectious disease, cancer, autoimmune disease, cardiovascular disease.	Are you on any IV or other serious medications, such as chemotherapy? [yes/ no]	X
Protocol Language: Patients who have undergone major abdominal, thoracic, spine or CNS surgery in the last 2 months, or plan to undergo surgery during study participation.	Have you had any surgery in the last two months? [yes/ no]	X
Protocol Language: Patients currently taking digoxin	Do you take the medication, digoxin or lanoxin? [yes/ no]	X

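### PATCH 3 does not exclude workers with a known earlier positive test or COVID-19 diagnosis, although its primary endpoint is conversion to a positive test

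*Combined protocol and SAP*

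**What the plan says.** Section 3.1 admits a PATCH 3 worker who is "asymptomatic and presumed negative for COVID-19 (no confirmatory testing conducted"). The Synopsis and Section 4.0 (PATCH 3 procedure, step 2) say the same.

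The combined exclusion list has no item on past infection. The nearest concerns drug exposure: "Receiving any trial treatment drug for 2019-nCoV within 14 days prior to screening evaluation (off label, compassionate use or trial related"). The catch-all is "Deemed unable to participate for medical reasons identified by Co-PI and study staff", which does not name previous COVID-19. The registration data in Section 4.0 include chronic medical problems but not COVID-19 history.

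In Appendix 4, Table A, the portal asks "Are you currently asymptomatic and presume not to have COVID", excluding on NO. It also asks "Have you been tested for COVID-19? [yes/ no"], again excluding on NO, and never asks the result. Parts B and C of that job aid do not ask about previous COVID-19.

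Section 8.4 names the measure on which the primary endpoint rests: "The rate of conversion to receiving a positive COVID-19 test result in each arm at the 2-month mark". Section 15.1 defines evaluability without reference to infection before entry: "Participants who received at least one continuous week of HCQ will be evaluable for the primary outcome". Section 16.1 removes nobody for earlier infection. Under Section 4.0 (step 11), virus and serology testing on Day 61 to 63 applies to those still undiagnosed. The plan does not say whether a worker diagnosed before entry counts as undiagnosed, or how a positive in that worker would be scored.

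**The concern.** Conversion presupposes a negative starting point. A recovered worker with a documented positive test can be symptom-free and presumed negative today, pass the portal, be randomised to up to 60 days of study tablets and remain in the analysis. The situation is foreseeable: the sub-study recruits staff with significant exposure, and Sections 2.1 and 16.1 themselves cite high infection rates among hospital workers at the epicentre.

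Two consequences are possible. If these workers have no new event, they add participants without events to both arms and lower power. If a residual positive swab is scored as a new infection, events unrelated to prevention enter both arms and pull the odds ratio toward 1. In either case people are given study tablets for a question about first infection that they cannot help to answer. The point concerns only a past result the worker already knows, which one question would reveal. It does not ask for testing at entry.

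**Working it through.** **Inputs from Section 16.1:** 175 per arm; 10% on placebo and 1% on HCQ; one-sided alpha 0.05; z for the log odds ratio; looks at information 0.25, 0.50 and 1.00; efficacy z 2.9473, 2.5825, 1.6664; futility z −1.2318 and −0.2676 at the two interims. **Assumed:** f, the fraction of enrolees with known earlier infection, equal in both arms, at 5%, 10% and 20% (17.5, 35 and 70 of 350). The documents give no figure for f.

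**The plan's own figure.** With placebo rate p_C and HCQ rate p_H:

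- log OR = ln[p_C/(1 − p_C)] − ln[p_H/(1 − p_H)] = −2.197 + 4.595 = 2.398, so the HCQ-to-placebo OR is 0.091.
- SE = √[1/(175 × 0.10 × 0.90) + 1/(175 × 0.01 × 0.99)] = √(0.0635 + 0.5772) = 0.800.
- Drift = 2.398/0.800 = 2.996.
- Integrating over the three looks with the printed boundaries, futility applied, gives power 90.6%.

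The stated power of at least 80% therefore holds as a lower bound. It is not reproduced as the actual power, which does not matter for this point. Overall one-sided alpha with futility ignored is 0.050, as intended.

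**Case 1: no new events in previously infected workers.** Rates become 0.10(1 − f) and 0.01(1 − f).

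| f | Rates, placebo vs HCQ | OR | Drift | Power |
|---|---|---|---|---|
| 0 | 10.0% vs 1.00% | 0.091 | 2.996 | 90.6% |
| 5% | 9.5% vs 0.95% | 0.091 | 2.915 | 89.2% |
| 10% | 9.0% vs 0.90% | 0.092 | 2.833 | 87.7% |
| 20% | 8.0% vs 0.80% | 0.093 | 2.662 | 83.9% |
| 30% | 7.0% vs 0.70% | 0.094 | 2.483 | 79.1% |

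Power passes 80% just below f = 30%. Simulation of the same design agrees to within 0.1 point.

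**Case 2: 10% of previously infected workers scored positive in each arm.** The 10% is also an assumption. Rates become 0.10(1 − f) + 0.10f = 10% on placebo and 0.01(1 − f) + 0.10f on HCQ.

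| f | Rates, placebo vs HCQ | OR | Drift | Power |
|---|---|---|---|---|
| 10% | 10.0% vs 1.9% | (0.019/0.981)/(0.10/0.90) = 0.17 | 2.872 | 88.4% |
| 20% | 10.0% vs 2.8% | (0.028/0.972)/(0.10/0.90) = 0.26 | 2.582 | 81.8% |

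**Limit of the approximation.** Only 175 × 0.01 = 1.75 HCQ events are expected, and the chance of none is 0.99^175 = 17.2%. The Wald log odds ratio is then not finite. If that outcome is counted as no rejection, exact single-look power in Case 1 is 82.1%, 78.1% and 73.0% at f = 0, 10% and 20%. Handling of an empty cell is a separate weakness, present already at f = 0, but earlier-infected workers make it more likely (0.991^175 = 20.6% at f = 10%).

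**The case against.** The strongest reply is that the effect is small. Section 16.1 promises at least 80% power, and under the plan's own 10% versus 1% every case up to f = 20% in the two tables stays above that. On a pooled z-test of the two rates, which the power sentence in Section 16.1 can be read to mean, power only goes from 98.2% to 97.0% at f = 10% and 95.2% at f = 20%. Randomisation balances these workers, so dilution leaves the odds ratio almost unchanged. Section 16.1 also gives 10% as the rate for enrolled workers. If that already allows for some past infection, multiplying by (1 − f) counts it twice. All of this stands, and it limits the priority.

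The portal evidence is also imperfect. PATCH 3 Table A excludes workers without recent fever while requiring them to be asymptomatic, and its last four rows match the PATCH 2 table, so the testing row looks carried over. The enrolment flow in Appendix 2 is a figure not available here, so a history question there cannot be ruled out. The words in brackets in Section 3.1 might be read as never tested, but the portal row that removes untested workers contradicts that. The discretionary exclusion could be used, but a recovered worker presents no evident medical reason.

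Three stronger readings are tempting but unsupported:

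- **That recovered workers can have no event.** The documents say nothing about immunity or reinfection, and the endpoint is any positive by an accepted test.
- **That every recovered worker would be scored positive through Day 61 to 63 serology.** That would take power to 81%, 67% and 46% at f = 5%, 10% and 20%. But Section 15.2 defines infection by measurement of SARS-CoV-2, and end-of-study testing is for the undiagnosed, which arguably leaves out a worker with a documented diagnosis.
- **That all of these workers receive HCQ and are counted.** Allocation is 1:1, so about half receive placebo, and Section 15.1 read literally does not define the placebo denominator at all.

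**Conclusion.** The gap is real. Nothing in the entry criteria, exclusions, registration data or portal table removes a worker with a known earlier positive test or diagnosis, and the analysis sections do not deal with such a worker afterwards, although the endpoint is defined as conversion.

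Its size is modest. As dilution it costs about 1, 3 and 7 points of power at an assumed 5%, 10% and 20% of enrolees and does not distort the odds ratio. On the large-sample log odds ratio calculation, power remains above 80% until nearly 30%. Scoring old infections as new matters more for the estimate: an odds ratio of 0.09 becomes about 0.17 or 0.26 under the assumed 10% re-positive rate.

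These figures rest on the assumed f, on balance between arms, on 10% being the rate in workers not previously infected, and on the normal approximation with very few HCQ events. Low to moderate priority, justified mainly because the remedy costs so little.

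**What to change.** Add to the PATCH 3 criteria in Section 3.1, and wherever they are repeated (Synopsis; Section 4.0, step 2), an exclusion for anyone reporting a previous positive SARS-CoV-2 test or a previous COVID-19 diagnosis. In Appendix 4, Table A, put a question on that history, excluding on YES, in place of the row that asks whether the person has been tested and excludes on NO.

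The cost is one criterion, one portal question and a small loss of recruits. To enrol 350 workers without such a history, 350/(1 − f) otherwise eligible workers are needed: 369, 389 or 438 at f = 5%, 10% or 20%. The change needs no baseline sampling, so it respects the decision not to test at entry. For the same reason it will not catch past infection that was never diagnosed.
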